NIDCR	National Institute of Dental and Craniofacial Research
OHRQoL	Oral Health-Related Quality of Life
P-CPQ	Parental-Caregiver Perception Questionnaire
P-CPQ EW	Parental-Caregiver Perception Questionnaire Emotional Well-Being
P-CPQ FL	Parental-Caregiver Perception Questionnaire Functional Limitations
P-CPQ SW	Parental-Caregiver Perception Questionnaire Social Well-Being
PP	Per protocol
PT	Preferred Term
SAE	Serious adverse event
SAP	Statistical Analysis Plan
SD	Standard Deviation
SDF	Silver Diamine Fluoride
S-ECC	Severe-Early Childhood Caries
SOC	System Organ Class
TEAE	Treatment Emergent Adverse Event
TFL	Tables, Figures, Listings
UP	Unanticipated Problem

1. INTRODUCTION

There are large disparities in the access to and effectiveness of many available preventive strategies for Severe-Early Childhood Caries (S-ECC) and Early Childhood Caries (ECC), two of the disease presentations for dental caries in children, one of the most common chronic diseases of childhood. This inequity frequently results in progression of dental disease in higher risk groups to an advanced stage, during which cavitated carious lesions and/or pulpal infections develop. When primary prevention fails or is not accessible, effective treatments that are safe, simple, low-cost, and acceptable to patients are necessary to decrease disease morbidity.

The product, 38% percent Silver Diamine Fluoride (SDF; also known as Diamine Silver Fluoride- DSF) is a potentially safe, non-invasive, quick, simple to use agent that will be tested in this trial for its ability to arrest cavitated lesions with exposed dentin in primary teeth [[Chu et al., 2002](#); [Llodra et al., 2005](#); [Tan et al., 2010](#); [Liu et al., 2012](#)]. SDF has been used since the 1970s in Asia as a caries arresting and anti-hypersensitivity agent, and in 2014 SDF was cleared by the Food and Drug Administration (FDA) as a medical device to manage hypersensitive teeth in adults. SDF is currently marketed in the United States as Advantage ArrestTM, an FDA approved device to manage dentin hypersensitivity in adults. The effectiveness of SDF will be compared to a placebo for arrest of cavitated lesions with dentin exposed in primary teeth, an off-label use of the current FDA premarket clearance for SDF.

The primary aim of this trial is to assess the efficacy of 38% SDF applied once, to arrest cavitated lesions (caries lesions with cavities that expose dentin clinically, but with no pulp exposure, pain, mobility, or clinical signs of pulpal infection) in the primary dentition (assessed using the International Caries Detection and Assessment System-ICDAS II activity criteria) at 6-month follow-up.

This statistical analysis plan (SAP) document details the planned statistical analyses to answer the study objective(s) for Study 17-094-E. The proposed analyses are based on the contents of protocol v3.1 (dated 16 April 2019). Populations for analysis, data handling rules, statistical methods, and formats for data presentation are provided. The statistical analyses and summary tabulation described in this SAP will provide the basis for the results sections of the Clinical Study Report (CSR) for this study.

2. OVERALL STUDY DESIGN AND PLAN

This trial is a Phase III, multisite, randomized, placebo-controlled superiority trial, with two parallel groups: SDF and placebo, applied at baseline and at approximately 6 months. The primary hypothesis of the trial is that 38% SDF is superior to placebo for arresting cavitated caries lesions with dentin exposed in primary teeth when assessed approximately 6 months after initial application.

An interim analysis will be performed, where the trial may be stopped early if interim analysis results provide early determination of efficacy or futility. Further details are described in [Section 8](#).

3. TRIAL OBJECTIVES AND OUTCOME MEASURES

The trial objectives are as follows:

- Aim 1: The primary aim of this trial is to assess the efficacy of 38% SDF applied once, to arrest cavitated lesions (caries lesions with cavities that expose dentin clinically, but with no pulp exposure, pain, mobility, or clinical signs of pulpal infection) in the primary dentition (assessed using the International Caries Detection and Assessment System-ICDAS II activity criteria, Appendix A) at 6-month follow-up.
- Aim 2: The first secondary aim is to assess the efficacy of 38% SDF applied twice, approximately 6 months apart, to arrest cavitated lesions in the primary dentition at approximately 8 months after initial application. A comparison of the effect of one application will be assessed over time at 3- and 6-month follow-ups (Sub-Aim 2a).
- Aim 3: The next secondary aim is to assess the impact of 38% SDF applied twice, approximately 6 months apart, on pain in children through use of the Dental Discomfort Questionnaire. The impact of 38% SDF on pain after a single application will be assessed at approximately 3 and 6 months (Sub-Aim 3a).
- Aim 4: The tertiary aim is to assess the effect of 38% SDF applied once (assessed at approximately 6 months after initial application) and twice, approximately 6 months apart (assessed at approximately 8 months after initial application), on family-level outcomes, assessing the impact on oral health-related quality of life (Sub-Aim 4a), and on treatment satisfaction and acceptability (e.g., associated with the change in color of treated lesions, etc.; Sub-Aim 4b). The relationship between treatment satisfaction/acceptability and other factors (e.g., family experience with ECC, oral hygiene and dietary habits) will be evaluated.

Additionally, safety will be assessed.

3.1. Primary Outcome Measure

The following primary efficacy outcome will be assessed:

- Efficacy of 38% SDF to arrest Cavitated Caries Lesions (Aim 1): Lesion arrest will be assessed for all cavitated lesions in the mouth (whether included or not in the trial, to reduce bias) using the ICDAS II system activity criteria, which categorizes lesion activity for ICDAS scores 5-6 based on dentin hardness [i.e., arrested lesions will change over time from soft-included in the trial at baseline- to hard, without an increase in ICDAS severity score (see Protocol Appendix A)]. The primary outcome will be the proportion of arrested trial lesions per child in each treatment arm. For the purposes of testing the hypothesis, the primary outcome will be measured at about 6 months post initial treatment (Aim 1).

3.2. Secondary Outcome Measures

The following secondary outcomes associated with application of 38% SDF will be assessed (*key secondary endpoints to be tested in a secondary endpoint hierarchical strategy as described in Section 6.11.4 are italicized*):

- *Efficacy of 38% SDF to arrest Cavitated Caries Lesions when applied twice, approximately 6 months apart: lesion arrest will be measured at approximately 8 months post initial treatment to assess efficacy (Aim 2).* Compare (Sub-Aim 2a) the effect of one application of SDF measured at approximately 3 and 6 months post initial treatment.
- *Child's Pain (Aim 3): The pain outcome will be defined as the proportion of children in each treatment arm experiencing toothache pain.* Additional pain outcomes will be the number of episodes of pain associated with treated teeth for each child in each arm during the follow-up period and the average recorded pain score for children in each treatment arm. The presence of pain associated with a trial tooth will be defined as a score of 1 or higher using the Dental Discomfort Questionnaire (DDQ; See Protocol Appendix B and Section 8), which a trial examiner can associate with a trial tooth during a clinical visit. The number of pain episodes is the total of all in-person visits at which a DDQ score of 1 or higher is confirmed by the trial examiner to be associated with a trial tooth. The pain score will be calculated using the DDQ.

3.3. Tertiary Outcome Measures

The following tertiary outcomes associated with the effect of 38% SDF on the Family will be assessed:

- Oral Health-Related Quality of Life (OHRQoL): OHRQoL will be assessed at baseline, 3-, 6-, and 8-month visits. Parents/legal guardians will be asked to complete the 16-item Parental-Caregiver Perception Questionnaire (P-CPQ) and 8-item Family Impact Scale (FIS) questionnaire (See Protocol Appendix C). The P-CPQ and FIS total and subscale scores are computed by summing the scores.
- Treatment Satisfaction and Acceptability: This will be assessed at baseline/24-48 hour contact/visit, and 3-, 6-, and 8-month visits using the questionnaire labeled as Family Survey (See Protocol Appendix D). Parents/legal guardians in each treatment arm will be asked about their level of satisfaction with the appearance of their children's teeth, and their overall level of acceptance and satisfaction with the treatment received. They will also be asked about their family experiences with ECC, as well as the child's brushing and dietary habits, and these items will be correlated with acceptability and satisfaction (e.g., adults having prior experience with the consequences of ECC and associated stress might be more accepting of this treatment alternative). In addition, color of treated lesions will be determined (yellow, brown, black), not as a primary indicator of lesion activity, but the change in color over time will be used for both trial arms as a measure of consequences associated with treatment assessed in the satisfaction questionnaire.

3.4. Safety Outcome Measures

Safety will be assessed through adverse events (AEs). AEs will be monitored throughout the trial. All AEs, serious adverse events (SAEs), and unanticipated problems (UPs) will be captured any time after informed consent is obtained. In addition, all AEs will be captured until 7 days after the last day of trial participation. Serious adverse events will be captured until 30 days after trial participation.

4. SAMPLE SIZE

The population will be children 12-71 months of age at the baseline caries examination attending early childhood education programs or recruited from clinics associated with the Michigan, Iowa or New York clinical trial sites.

The primary outcome of this trial is the proportion of arrested caries lesions approximately 6 months from the baseline visit (i.e., lesions that have changed from soft to hard over the trial period according to the ICDAS II activity criteria). A 10% difference in the proportion of arrested caries lesions between the SDF and placebo groups will be considered clinically significant. Prior studies in the literature of SDF using this outcome in primary cavitated lesions have shown a wide range for the proportion of arrested caries lesions for both SDF-treated and placebo-treated or untreated lesions; therefore the 10% difference in proportions was calculated assuming 55% versus 45% arrested caries lesions for SDF compared to placebo. In prior studies, an average of 4 lesions was treated per participant, with a within-participant correlation of 0.5; we are conservatively assuming 3 lesions per participant. The sample size calculations used a 2-sided test for a difference in proportions with cluster randomization (participant as the cluster) at significance level $\alpha=0.1\%$, with 80% power to detect a superiority difference of 10% for SDF compared to placebo. The calculations also account for the use of an early stopping rule for efficacy and futility. The interim analysis will be performed after approximately half of the sample has completed the 6-month examinations. A Lan-Demets spending function with an O'Brien-Fleming type boundary will be used, with p-values for efficacy at 0.000001709 and 0.00099938 at 50% and 100% completion, respectively. Non-binding p-values for stopping due to futility at 50% and 100% completion will be 0.2336928 and 0.00099938, respectively. With the above assumptions, the trial will require 1144 participants to be enrolled. Sample size calculations were made using East version 6.

5. RANDOMIZATION

Randomization will be allocated to SDF/Placebo in a 1:1 fashion and will be stratified by site. Randomization to 38% SDF application (treatment) or placebo (control) will be at the participant-level; all teeth within a participant will receive the same trial product. Both treatment and control will be dispensed from identical unit-dose ampules coded and labelled to ensure masking of all trial personnel. Randomization will occur after the baseline ICDAS exam is completed and it is verified that the child has eligible trial teeth.

The randomization schedule will be generated by a designated unmasked biostatistician. The Project Biostatistician will remain masked to the trial randomization until after database lock and unblinding.

Additional details can be found in the study Randomization Plan.

6. PLANNED ANALYSES

No SAP prepared in advance of the data can be definitive, and the final CSR may contain additional tables or statistical tests, if warranted by the data obtained. The justification for any such additional analyses, or modifications to any planned analyses, if applicable, will be fully documented in the final CSR.

6.1. Statistical Comparisons

All statistical comparisons will be made using a two-sided test. The interim and final analyses will be conducted using p-value thresholds of 0.000001709 and 0.00099938, respectively, for the primary analysis. The overall type I error for interim and final primary endpoint analysis is two-sided $\alpha=0.1\%$.

6.2. Analysis Populations

There are 5 analysis populations as described in the following sections. Participants excluded from the analysis populations and the reason for their exclusion will be listed in Appendix 16.2 of the CSR.

6.2.1. Intent-to-Treat (ITT) Population

The ITT Population will include all participants who are randomized to receive study drug. Participants will be summarized according to their randomized treatment and not the treatment they receive. The ITT Population will be used for efficacy analyses.

6.2.2. Per Protocol (PP) Population

The PP Population will be limited to subjects who complete the baseline, 3-month, and 6-month dental examinations within the originally-specified windows. The PP Population will be used for supportive analyses of efficacy.

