6.2.5. Per Protocol Population #2 (PP2) - Interim Participants

The PP2 Population will be limited to subjects included in the interim analysis who complete the baseline, 3-month, and 6-month dental examinations within the originally-specified windows. The PP2 Population will be used for supportive analyses of efficacy.

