6.11. Efficacy Analyses

All efficacy endpoints will be analyzed using the ITT and ITT2 populations. Additional analyses will be performed on the PP and PP2 populations.

The null hypothesis is no difference between the treatment groups and the alternative hypothesis is there is a difference between treatment groups. All statistical comparisons will be made using a two-sided test. The interim and final analyses will be conducted using p-value thresholds of 0.000001709 and 0.00099938, respectively. The overall type I error for interim and final primary endpoint analysis is two-sided $\alpha=0.1\%$.

Several categorical variables that are to be used as covariates in the GEE model will have categories collapsed due to small sample sizes. Race and ethnicity will be combined to form a single combined variable defined as: Hispanic or Latino if a subject indicated as such for ethnicity, multiracial if more than one race was selected, Black, White, “Asian or ‘American Indian or Alaska Native’ or ‘Native Hawaiian / Other Pacific Islander’”, “Not Reported” or Unknown”. Within the ‘tooth’ variable, lower incisors (LL1, LL2, LR1, LR2) will be combined into a single category and LR6 will be combined with LR5 for the imputation models for the lesion arrest outcomes, and combined into upper jaw / lower jaw and anterior teeth (upper and lower central incisors, lateral incisors, and canines) / posterior teeth (upper and lower molars on the) variables for the imputation models for the presence of tooth pain outcomes. For the imputation models for the presence of tooth pain outcomes, child ages 1 and 2 years will be combined.

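### As written, the PP and PP2 sets could serve supportive analyses of the two-application 8-month endpoint without requiring the second application or an in-window 8-month examination

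*SAP*

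**What the plan says.** SAP 6.2.2 states: "The PP Population will be limited to subjects who complete the baseline, 3-month, and 6-month dental examinations within the originally-specified windows". SAP 6.2.5 repeats the rule for the interim subset: "The PP2 Population will be limited to subjects included in the interim analysis who complete the baseline, 3-month, and 6-month dental examinations", again within the original windows. Neither section mentions application of trial product or the 8-month examination.

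On use, SAP 6.2.2 says: "The PP Population will be used for supportive analyses of efficacy". SAP 6.11 says: "All efficacy endpoints will be analyzed using the ITT and ITT2 populations". It then adds: "Additional analyses will be performed on the PP and PP2 populations". The PP sentence names no endpoint and excepts none.

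SAP 3.2 gives the first key secondary endpoint as: "Efficacy of 38% SDF to arrest Cavitated Caries Lesions when applied twice, approximately 6 months apart: lesion arrest will be measured at approximately 8 months". SAP 6.11.4 tests it first in the secondary hierarchy. The second key secondary endpoint, lesion pain, is also assessed at 8 months.

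The per-protocol rule in Protocol 12.4.1 was stricter. It required examinations and questionnaires at baseline, 3, 6 and 8 months, plus the three intermediate contacts, all within window. It did not require an application either. SAP 9 records that the definition was updated and gives no reason. The SAP defines no separate 8-month per-protocol set.

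**The concern.** A per-protocol analysis of a two-application endpoint is normally read as showing what happens when both applications are given and the outcome is observed on time. Membership here is settled by the 6-month examination. The second application and the 8-month examination are the two events that distinguish the 8-month endpoint from the 6-month one, and both fall outside the rule.

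What is at stake is interpretation. A supportive result for the first key secondary endpoint could carry the per-protocol label while including once-treated children, and children whose 8-month result was never observed in window. A reader comparing it with the ITT result could not tell how far the comparison speaks to adherence to the two-application regimen.

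**Working it through.** **1. The plan's own figures.** The documents give no size, power or expected composition for PP or PP2, and none for the 8-month endpoint. The one stated sample size, 1144, is for the 6-month primary endpoint and does not involve the PP rule. It reproduces as follows:

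- Lesions per arm, fixed design: (0.55 × 0.45 + 0.45 × 0.55) × (3.2905 + 0.8416)² / 0.10² = 0.495 × 17.075 / 0.01 ≈ 845.2.
- Design effect: 1 + (3 − 1) × 0.5 = 2, so children per arm = 845.2 × 2 / 3 ≈ 563.5.
- Inflation for the stated efficacy and futility boundaries, solved numerically with the futility p-value read as two-sided: 1.0135. This gives 571.1, rounded up to 572 per arm and 1144 in total.

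Nothing below changes that figure.

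**2. The rule against the endpoint.**

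| Element of the 8-month endpoint | Protocol 12.4.1 | SAP 6.2.2 and 6.2.5 |
|---|---|---|
| First application | not listed | not listed |
| Second application | not listed | not listed |
| In-window 6-month examination | required | required |
| In-window 8-month examination | required | not required |

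**3. Can a PP child lack these elements?**

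- *First application.* Hardly. Protocol 5.5.1 withdraws a child whose baseline examination or application is not completed, so anyone with in-window 3- and 6-month examinations should have had it.
- *Second application.* Yes. Protocol 7.3.5 places it at the 6-month visit, after medical eligibility is confirmed. Protocol 16.6 lists an examination not performed and product not applied as distinct items within its deviation examples. SAP 6.10 tabulates exposure as 0, 1 or 2 applications. Completing the 6-month examination therefore does not establish re-application.
- *8-month examination.* Yes. SAP 6.4.2 reports that the pandemic kept some children from in-person visits within the windows, and that telephone contacts could not include dental examinations.

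**4. What happens to a PP child with no 8-month result.** SAP 6.11 makes multiple imputation the main method for missing 6- and 8-month efficacy data. If that carries over to PP analyses, which the SAP does not state, the result would be imputed. The number of applications received is not among the listed predictors of lesion arrest. The share affected is not given. The 10% attrition in Protocol 12.2 covers the whole trial, whereas PP children have already been seen at month 6.

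**5. Illustration of dilution.** Let f be the share of SDF-arm lesions in the PP set belonging to children without the second application (assumed). Protocol 2.2 cites literature arrest of about 79% after one application and 91% after a repeat. Then:

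SDF arrest in PP = (1 − f) × 91% + f × 79%, and dilution = f × 12 points.

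| f (assumed) | SDF arrest in PP | Dilution (points) |
|---|---|---|
| 2% | 90.8% | 0.2 |
| 5% | 90.4% | 0.6 |
| 10% | 89.8% | 1.2 |
| 15% | 89.2% | 1.8 |
| 20% | 88.6% | 2.4 |

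If a second placebo application makes no difference, the between-arm difference shrinks by the same amount. For scale, SAP 4 treats 10 points as clinically significant.

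**The case against.** The strongest reply is that no sentence assigns PP or PP2 to the 8-month endpoint. In SAP 6.11 the reference to all efficacy endpoints belongs to the ITT and ITT2 sentence, and the following PP sentence names none. The definition suits the 6-month primary endpoint and may have been written for it. This stands as a limit: use at 8 months is read from unrestricted wording. It does not remove the point, because nothing in SAP 6.2.2, 6.2.5 or 6.11 confines the sets to 6 months.

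Second, re-application is part of the same 6-month visit that PP requires, so most PP children will probably have received it. That also stands. Missed second applications are foreseen, but nothing shows them to be common. A reader might infer that treatment receipt is unsecured at both visits; Protocol 5.5.1 in effect secures the first.

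Third, the dilution is small, rests on an assumed share and on literature rates rather than the design rates of 55% and 45%, and in the illustration works against SDF, which is conservative for superiority. This is correct, and the figures should not be read as an estimate of bias in this trial.

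Fourth, requiring the second application and an 8-month examination without exception would remove children whose trial teeth left early for pain or infection. Protocol 7.3.3 and SAP 6.11.1 count these as failures, so the set would be selected on outcome. This stands and shapes the fix.

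A reader might also call the 3-month examination condition an error, since no product is applied then. The documents do not support that. Protocol 12.4.1 had the same condition, and the examination feeds the 3- and 6-month comparisons. Adherence to the examination schedule is a legitimate meaning of per protocol.

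**Conclusion.** The point holds in limited form. Followed as written, the SAP permits a supportive per-protocol analysis of two-application arrest at 8 months that includes children without the second application or without an in-window 8-month examination. The SAP removed the examination requirement that the protocol had; the absence of an application criterion was inherited from the protocol. The 8-month pain endpoint has the same gap.

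The numerical effect cannot be derived from the documents. The 0.6 to 1.8 point range depends on an assumed 5% to 15% lacking the second application and on the 79% and 91% literature rates carrying over. A reader might infer that the conclusion on the first key secondary endpoint is compromised; it is not. SAP 6.2.1 and 6.11 make ITT the efficacy population, PP and PP2 are supportive, and the ITT results, alpha and gatekeeping do not depend on them.

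**What to change.** Keep the present PP and PP2 definitions for endpoints through 6 months. In SAP 6.2.2 and 6.2.5, add an 8-month PP set and an 8-month PP2 set, to be used for the 8-month endpoints, which also require:

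- receipt of the assigned product at the second application; and
- an 8-month dental examination within the original window.

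State that children or lesions that left under the early exit strategy remain in the 8-month sets as treatment failures, in line with SAP 6.11.1. They should be exempt from application and examination conditions falling after the exit. In SAP 6.11, name which set serves which endpoint.

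The simpler alternative is one sentence in SAP 6.11 limiting PP and PP2 analyses to endpoints through 6 months.

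The first option costs some SAP wording, one extra population flag and a smaller 8-month per-protocol set. The second costs only wording but leaves the 8-month endpoints without a per-protocol analysis. Dropping the 3-month examination condition is optional and not part of this correction.

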5.2 Participant Exclusion Criteria

An individual who meets any of the following criteria will be excluded from participation in this trial:

Child:

- Hereditary generalized developmental dental defects such as Amelogenesis Imperfecta and Dentinogenesis Imperfecta.
- Known allergy/sensitivity to silver or other heavy metal ions.
- Presence of any gingival or peri-oral ulceration, abscess or stomatitis.
- Participating in the foster care system at trial initiation.
- Toothache pain at baseline (based on Dental Discomfort Questionnaire score of 1 or higher (Appendix B)).
 - Note: If toothache pain occurs after baseline, the child remains eligible to continue in the trial as long as he/she has at least one trial tooth that meets tooth inclusion/exclusion criteria.
- Demonstrated inability to comply with trial protocol requirements (determination is at the Clinical Site Investigator’s discretion).
- Rickets.
- Osteopenia or osteoporosis (e.g., Osteogenesis Imperfecta, Ehlers-Danlos Syndrome, Marfan Syndrome, etc.).
- Chronic diseases such as chronic kidney disease, leukemia, lymphoma, rheumatic disorders, etc.
- Metabolic bone disease (e.g., Galactosemia, Glycogen Storage Disease Type 1, etc.).

- Chronic glucocorticoid, anticonvulsants, chemotherapy, bisphosphonate administration.
- Hypothyroidism, hyperparathyroidism, impaired glucose tolerance, hypocalcemia or hypophosphatemia.

Tooth:

- Pain due to caries at baseline (based on DDQ score of 1 or higher, Appendix B).
 - Note: If toothache pain occurs after baseline due to a trial tooth, the tooth is removed from the trial.
- Pulpal exposure, or signs of pulpal infection (abscess, fistula, swelling).
- Mobility not associated with expected exfoliation patterns.

Parent/Legal Guardian:

- Demonstrated inability to comply with trial protocol requirements (determination is at the Clinical Site Investigator's discretion).
- Inability to read and comprehend the consent document or trial questionnaires in the translated languages available.

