6.11.1. Primary Efficacy Hypothesis, Endpoint, and Analysis

The primary efficacy hypothesis is that 38% Silver Diamine Fluoride (SDF) will arrest cavitated caries lesions (ICDAS 5 or 6) in primary teeth, measured by a change in dentin hardness, without a change in ICDAS severity score, after a single application (measured at 6 months). This occurs as a result of the halting of the caries disease process, which occurs very soon after application of SDF due to its strong antimicrobial and remineralizing properties.

The proportion of arrested cavities at the 6-month visit will be compared between the SDF and placebo-treated groups first using a generalized estimating equation (GEE) model with a logit link for the lesion-specific binary outcome yes/no lesion arrest at the 6-month visit, using an exchangeable correlation to account for non-independence among multiple treated lesions within a participant. The GEE model will include study site as a covariate due to stratified randomization by site.

Trial teeth that cause pain due to caries, pulpal exposure, mobility, signs of pulpal infection (abscess, fistula, swelling) will be exited from the trial and referred for appropriate care (early exit strategy), and will be considered treatment failures (non-arrest) in the analysis of the primary efficacy outcome. Treatment failures from the early exit strategy and timing of the early exit are determined from the subject disposition (withdrawal from the study with reasons related to adverse event or study tooth abscess, pulpal involvement, or pain), lesion withdrawal from the study (reason for lesion withdrawal study tooth abscess, fistula, pulpal involvement, or pain), lesion examination (notes for study tooth abscess, fistula, pulpal involvement, or pain), and adverse events. In short, any lesions removed from the trial due to the “early exit strategy” will be considered treatment failures – non-arrest of the lesion and presence of pain and/or infection – and thus will not be considered to be missing data.

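### The PP and PP2 definitions remove children withdrawn entirely before month 6 as early-exit failures, so these supportive analyses select on the outcome

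*SAP*

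**What the plan says.** - **Who is in PP (SAP 6.2.2).** "The PP Population will be limited to subjects who complete the baseline, 3-month, and 6-month dental examinations within the originally-specified windows". Its role is limited: "The PP Population will be used for supportive analyses of efficacy".
- **Who is in PP2 (SAP 6.2.5).** "The PP2 Population will be limited to subjects included in the interim analysis who complete the baseline, 3-month, and 6-month dental examinations", again within the initially defined windows.
- **Where these sets are used (SAP 6.11).** "All efficacy endpoints will be analyzed using the ITT and ITT2 populations. Additional analyses will be performed on the PP and PP2 populations".
- **How early exits are scored (SAP 6.11.1).** Teeth that leave under the early exit strategy "will be considered treatment failures (non-arrest) in the analysis of the primary efficacy outcome", "and thus will not be considered to be missing data". One listed source for identifying them is the child's own withdrawal from the study for an adverse event or for abscess, pulpal involvement or pain of a study tooth.
- **Estimand (SAP 6.11.2).** The intercurrent event is discontinuation of the study for pain before the 6-month visit, and it is set to failure.
- **Unit of exit (Protocol 5.2).** A trial tooth that becomes painful leaves the trial, but "the child remains eligible to continue in the trial as long as he/she has at least one trial tooth" that still meets the tooth criteria.

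The PP rule in Protocol 12.4.1 is stricter, since it also requires the 8-month visit, the questionnaires and the intermediate contacts. It too lacks an early-exit exception. SAP 9 records that the PP definition was updated.

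**The concern.** A per-protocol set should select on adherence. Here a child can follow the protocol exactly and still be excluded because the treatment failed. Take a child with one trial tooth who attends on time and whose tooth is exited at the 3-month visit. The outcome is known (non-arrest), but the child does not go on to a 6-month exam and so leaves PP. If the same failure were first found at an in-window 6-month visit, the child would stay. Membership therefore depends on whether, and when, the outcome was bad.

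At stake is the use of PP and PP2 as a check on the ITT result. Removing known failures raises arrest in both arms and can move the difference either way. A gap between PP and ITT could then reflect the exclusion rule rather than adherence. If the lesion-pain endpoint is repeated on PP, the rule would also remove pain events, because an exit for pain is itself the event.

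**Working it through.** **1. Who is affected**

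| Child | ITT/ITT2 | PP/PP2 |
|---|---|---|
| Some trial teeth exit, one stays eligible, exams in window | exited lesions are failures | kept, exited lesions are failures |
| Failure first found at an in-window 6-month visit | failure | kept, failure |
| Withdrawn entirely before the 6-month exam under early exit | failure | **dropped** |

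Only the last row is a problem.

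**2. The plan's own figure**

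Inputs (SAP 4): 55% versus 45%, two-sided alpha 0.001, power 80%, 3 lesions per child, within-child correlation 0.5.

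- Lesions per arm = [3.2905·√(2·0.5·0.5) + 0.8416·√(0.55·0.45 + 0.45·0.55)]² / 0.10² = 852.
- Design effect = 1 + (3 − 1)·0.5 = 2.0.
- Children per arm = 852·2.0/3 = 568, or 1136 in total for a fixed design.

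The stated 1144 is reproduced to within 1%. With both looks, power at 1144 is 80.1% or 80.7%, depending on whether the futility p-value is read as two-sided or one-sided. The PP rule plays no part in this.

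**3. Effect on PP**

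Let p be an arm's arrest proportion with early exits counted as failures, and f the share of that arm's lesions in whole-child exits before month 6. All dropped lesions are non-arrest, so

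PP arrest = p/(1 − f), and the gain in points = p·f/(1 − f).

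Other PP exclusions are assumed unrelated to arrest. Every f below is an assumption.

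| f SDF / placebo | PP SDF | PP placebo | Difference (points) | Odds ratio |
|---|---|---|---|---|
| none dropped | 55.0% | 45.0% | 10.0 | 1.494 |
| 2% / 5% | 0.55/0.98 = 56.1% | 0.45/0.95 = 47.4% | 8.8 | 1.421 |
| 5% / 10% (high) | 0.55/0.95 = 57.9% | 0.45/0.90 = 50.0% | 7.9 | 1.375 |
| 8% / 8% | 0.55/0.92 = 59.8% | 0.45/0.92 = 48.9% | 10.9 | 1.553 |
| 8% / 4% | 0.55/0.92 = 59.8% | 0.45/0.96 = 46.9% | 12.9 | 1.685 |

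**4. Direction**

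Placebo gains more points than SDF only if f_P/(1 − f_P) > (0.55/0.45)·f_S/(1 − f_S). The break-even placebo share is 6.0% when SDF has 5%, and 9.6% when SDF has 8%, about 1.2 times the SDF share. With equal exits of 8%, SDF gains 4.8 points and placebo 3.9, so the difference widens.

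**5. How large f might be**

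Assume 3 lesions per child and lesion exits that follow a beta-binomial with correlation 0.5. If a share q of lesions exits, the share of children who lose all three is q(1 + q)(2 + q)/6. For q of 4%, 8% and 12% this is 1.4%, 3.0% and 4.7%, so about 35% to 40% of exited lesions are in fully exited children. An f of 10% would need q near 22%: 0.22·1.22·2.22/6 = 0.099. That is why 5%/10% is labelled high.

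**The case against.** The case for leaving the text alone has real force.

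- **No decision rests on PP.** This is a superiority trial analysed on ITT and ITT2, and PP is supportive. Tipping-point and wider-window analyses are also planned (SAP 6.11.3). This stands, and it limits the severity.
- **Few children are likely to be lost.** SAP 6.11.5 drops several pain comparisons because so few participants had pain. Whole-child exits for pain are a subset of those, although infection exits could add some. This stands. The 8–12% in Protocol 2.3.1–2.3.2 and Appendix B describes emergency visits during a 6- to 9-month wait for the operating room. It is neither an exit rate nor given by arm.
- **Dropped children may carry little weight.** With correlation 0.5, a one-lesion child has weight 1 in the GEE and a three-lesion child 3/2 = 1.5. If 5% and 10% of children exit and all have one lesion, the weight shares are 0.05/(0.05 + 0.95·1.5) = 3.4% and 0.10/(0.10 + 0.90·1.5) = 6.9%. PP then shows 56.9% versus 48.3%, a difference of 8.6 rather than 7.9. This reduces the effect but does not remove it.

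Three stronger readings are tempting, and the documents do not support them.

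- **A reader might infer that every early-exit failure leaves PP.** Exit is by tooth (Protocol 5.2, 7.3.3, 7.3.4), so only children lost entirely before the 6-month exam are dropped.
- **A reader might infer that arrest is inflated most in the arm with more failures.** That always holds for the relative factor 1/(1 − f), but not in points. At the 2-week arrest of 72% versus 5% cited in Protocol 2.2, with assumed f of 4%/12%, SDF gains 0.72·0.04/0.96 = 3.0 points and placebo 0.05·0.12/0.88 = 0.7.
- **A reader might infer that PP cannot be interpreted at all.** SAP 6.5 already reports exclusions from each population by treatment group with reasons, so the number of early-exit exclusions can be seen.

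**Conclusion.** The point holds in a limited form. As written, SAP 6.2.2 and 6.2.5 remove children whom SAP 6.11.1 and 6.11.2 treat as known failures, so PP and PP2 select on the outcome. Each arm's PP arrest is too high by the factor 1/(1 − f), and the treatment difference can shrink or grow. In the scenarios shown it runs from 7.9 to 12.9 points against a true 10.0.

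These sizes rest on the planning arrest rates, on assumed exit shares that the documents do not give by arm, and on other PP exclusions being unrelated to arrest. With few exits the distortion would be small. The primary ITT inference, the stopping boundaries and the sample size are not affected. Severity is minor to moderate: a supportive analysis conflicts with the plan's own outcome rule.

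**What to change.** In SAP 6.2.2 and 6.2.5, define PP and PP2 as children who either

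- completed the baseline, 3-month and 6-month exams in window, or
- had an early-exit failure before the 6-month visit and completed in window all exams due up to the exit.

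Score the exited lesions as non-arrest, as SAP 6.11.1 already does. In the SAP 6.5 disposition table, show early exit as its own reason for exclusion or inclusion, by arm. If PP results under the present definition already exist, report both versions.

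The cost is one clause in each section and a change to the population flag. The disposition, lesion-withdrawal and visit-date data are already collected, so no new data are needed.
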